I. Dose Escalation Phase 1 Part of Study: The study will employ the standard “cohort of three” design (2). Three patients are treated at each dose level with expansion to six patients per cohort if DLT is observed in one of the three initially-enrolled patients at each dose level. If no DLT occurs after 2 doses, escalation to the next dose level will be permitted. The maximum tolerated dose is defined as the highest safely tolerated dose, where not more than one patient experienced DLT, with the next higher dose level having at least two patients who experienced DLT. Patients in the dose escalation study may continue treatment at their designated dose levels up to eighteen 3-week cycles or until significant disease progression or unacceptable toxicity occurs. No intra-patient dose escalation will take place.

Dose of nivolumab: 3 mg/kg IV over 30 min. q 3 weeks (Day 1 of every 21-day cycle)

Dose of ABI-009:

NB: ABI-009 will start after 2nd nivolumab dose and will be administered on D8 and D15 beginning in C2.

Escalating doses IV over 30 min for 2 of every 3 weeks:

Treatment Cycle	# Pts.	Dose Level	Dose, mg/m ²
Every 3 weeks	3-6	I	56
Every 3 weeks	3-6	II	75
Every 3 weeks	3-6	III	100

Note: DLT includes any \geq Grade 3 colitis, hepatitis, or pneumonitis, any Grade 1-2 colitis, hepatitis or pneumonitis that recurs, worsens or persists with oral steroids longer than 14 days, symptoms of adrenal crisis, any Grade 4 hematologic toxicity or any \geq Grade 3 non-hematologic toxicity. If DLT develops in more than 1 patient at Dose 56 mg/m², the dose will be de-escalated to 45 mg/m² and to 30 mg/m² if DLT develops at 45 mg/m².

II. Expansion Phase 2 Part of Study: Following dose escalation, an additional 22-28 patients will receive ABI-009 at the MTD and defined doses of nivolumab to assess overall safety and potential efficacy in a greater number of patients. Patients in the expansion phase of the study may continue treatment up to 18 3-week treatment cycles or until significant disease progression or unacceptable toxicity occurs.

The study will be conducted in compliance with International Conference on Harmonisation (ICH) Good Clinical Practices (GCPs).

Surgical Resection: After three or more treatment cycles, the principal investigator may recommend surgical debulking, complete surgical removal or a biopsy. If residual disease

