The following table gives the probability of dose escalation at a single dose level as a function of the true probability of DLT at that level using the cohorts of 3 design (Objective #1) (2).

Table 1. Probability of Dose Escalation

True Rate of DLT (%)	Probability of Dose Escalation
10	0.91
20	0.71
30	0.49
40	0.31
50	0.17

For the Phase 1 part of the study, the entire treated population (Full Analysis Set) will be the analysis population for all safety analyses. Adverse events will be coded using the NIH CTCAE v4.03. Summary tables will include the number and percentage of patients with AEs, serious AEs, fatal AEs and other AEs of interest. Safety will be analyzed in all patient groups together (metastatic and locally advanced). Although this study will not be large enough to allow firm conclusions about safety or efficacy, it will provide preliminary data on safety and efficacy that will be useful in planning future studies. Frequency tables, graphs, and summary statistics will be used for outcome data.

Patient incidence of all treatment-emergent AEs will be tabulated. Tables of fatal adverse events, serious adverse events, treatment-related AEs, and adverse events leading to withdrawal from investigation product will also be provided.

For ABI-009 and nivolumab exposure, summary statistics will be provided for total number of doses, average dose administered, and duration of each treatment.

Efficacy Analyses:

The disease control rate (DCR; CR+PR+SD), objective response rate (ORR; CR + PR), progression free survival (PFS), and recurrence-free survival (RFS) will be assessed by a local radiologic assessment using Response Evaluation Criteria in Solid Tumors (RECIST) v1.1 and irRECIST.

The focus of the study is to estimate the DCR in patients treated with ABI-009 and nivolumab. Patients who progress before receiving ABI-009 will be replaced, and will not be included in the statistical analysis. The number and percentage of patients achieving response will be summarized.

Analysis of other efficacy endpoints, PFS at 4 months, RFS at 4 months, median PFS, and median OS will be assessed for all subtypes together, and separately in the five sarcoma subtypes.

PFS, RFS and OS will be summarized using Kaplan-Meier (KM) analysis. The number of patients in each category is expected to be small; therefore, PFS at 4 months, RFS at 4 months, median PFS, median RFS and median OS for these patients will be summarized by descriptive statistics.

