End of Treatment	The date of the last dose of ABI-009 or nivolumab which ever is later for an individual patient.
End of Treatment Visit	For a patient is when safety assessments and procedures are performed after the last treatment, which must occur at least 4 weeks (\pm 7 days) after the last dose of ABI-009 or nivolumab whichever is later.
Primary Analysis	For this study will occur after all patients have either completed the study or completed 12 months of treatment. Patients who are still active at the time of the primary analysis may continue on study until disease progression or medication intolerance is observed.
Follow-up Period	The on-study time period after the End of Treatment Visit. All patients that discontinue study drug and have not withdrawn full consent to participate in the study will continue in the follow-up phase for survival and anticancer therapy. Follow up will continue approximately every 12 weeks (+/- 3 weeks), or more frequently as needed, until death, withdrawal of consent, or the study closes, whichever is the earliest. This evaluation may be made by record review and/or telephone contact.
Efficacy Analysis Dataset	All enrolled patients with measurable tumor per RECIST v1.1 at baseline who received at least two doses of ABI-009 and had a follow-up CT scan/MRI (modified treated population)
Full Analysis Set	All enrolled patients who receive at least one dose of ABI-009 (treated population).
Per-protocol Analysis Set	All enrolled patients who do not have any prospectively defined protocol violations.

Progression-free survival	The time from the first dose date to the first observation of a disease progression or death due to any cause.
Recurrence-free survival	The time from the first dose date to the first observation of disease progression or recurrence/progression after surgical resection, or death due to any cause.
Overall survival	The time from the first dose date to the date of death due to any cause.
Overall response rate	The proportion of patients who achieve a confirmed partial response or complete response per RECIST 1.1. Response rates based on a local radiologic assessment
Duration of response	The time from when criteria of response are first met until the first observation of disease progression per RECIST v1.1 or death due to any cause, whichever comes first.

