In Trial 1, where patients were evaluated at baseline and during the trial for thyroid function, Grade 1 or 2 hypothyroidism occurred in 8% (21/268) of patients receiving nivolumab and none of the 102 patients receiving chemotherapy. The median time to onset was 2.5 months (range: 24 days-11.7 months). Seventeen of the 21 patients with hypothyroidism received levothyroxine. Fifteen of 17 patients received subsequent nivolumab dosing while continuing to receive levothyroxine.

Grade 1 or 2 hyperthyroidism occurred in 3% (8/268) of patients receiving nivolumab and 1% (1/102) of patients receiving chemotherapy. The median time to onset in nivolumab-treated patients was 1.6 months (range: 0-3.3 months). Four of five patients with Grade 1 hyperthyroidism and two of three patients with Grade 2 hyperthyroidism had documented resolution of hyperthyroidism; all three patients received medical management for Grade 2 hyperthyroidism.

- **Any other severe or Grade 3 treatment-related adverse reactions**

Other clinically significant immune-mediated adverse reactions can occur. Immune-mediated adverse reactions may occur after discontinuation of nivolumab therapy.

The following clinically significant, immune-mediated adverse reactions occurred in less than 1% of nivolumab-treated patients in Trial 1: pancreatitis, uveitis, demyelination, autoimmune neuropathy, adrenal insufficiency, and facial and abducens nerve paresis.

Across clinical trials of nivolumab administered at doses of 3 mg/kg and 10 mg/kg the following additional clinically significant, immune-mediated adverse reactions were identified: hypophysitis, diabetic ketoacidosis, hypopituitarism, Guillain-Barré syndrome, and myasthenic syndrome.

Nivolumab was discontinued for adverse reactions in 9% of patients. Twenty-six percent of patients receiving nivolumab had a drug delay for an adverse reaction. Serious adverse reactions occurred in 41% of patients receiving nivolumab. Grade 3 and 4 adverse reactions occurred in 42% of patients receiving nivolumab. The most frequent Grade 3 and 4 adverse reactions reported in 2% to less than 5% of patients receiving nivolumab were abdominal pain, hyponatremia, increased aspartate aminotransferase, and increased lipase. Other adverse events that occurred in $\geq 10\%$ of patients were rash, pruritus, cough, upper respiratory tract infection, peripheral edema, increased AST, increased alkaline phosphatase, hyponatremia, increased ALT, and hyperkalemia, with

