8.2. Safety Analysis

Demographic and baseline information (e.g., extent of prior therapy) on study patients will be tabulated. The number of patients studied for the Phase 1 part of study could range from 12 to 18 evaluable patients, and 22-28 evaluable patients for the Phase 2 part of the study.

For the Phase 1 part of the study, the following information will be reported for adverse events observed in the study: dose level, type (organ affected or laboratory determination, such as absolute neutrophil count), severity (by NCI Common Terminology Criteria for Adverse Events (CTCAE) Version 4.03 and most extreme abnormal values for laboratory determinations) and relatedness to study treatment. For each dose the number and percentage of patients experiencing any grade 3, 4, or 5 adverse event will be reported, as well as the number and percentage of patients who experienced selected specific types of adverse events. In addition, the DLTs will be summarized by dose level and the MTD will be determined.

The following table gives the probability of dose escalation at a single dose level as a function of the true probability of DLT at that level using the cohorts of 3 design (Objective #1) (2).

Table 1. Probability of Dose Escalation

True Rate of DLT (%)	Probability of Dose Escalation
10	0.91
20	0.71
30	0.49
40	0.31
50	0.17

For the Phase 2 part of the study, the entire treated population (Full Analysis Set) will be the analysis population for all safety analyses. Adverse events will be coded using the NIH CTCAE v4.03. Summary tables will include the number and percentage of patients with AEs, serious AEs, fatal AEs and other AEs of interest. Safety will be analyzed in all patient groups together (metastatic and locally advanced). Although this study will not be large enough to allow firm conclusions about safety or efficacy, it will provide preliminary data on safety and efficacy that will be useful in planning future studies. Frequency tables, graphs, and summary statistics will be used for outcome data.

Patient incidence of all treatment-emergent AEs will be tabulated. Tables of fatal adverse events, serious adverse events, treatment-related AEs, and adverse events leading to withdrawal from investigation product will also be provided.

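### The safety population requires an ABI-009 dose, so patients who stop or die during the four-week nivolumab lead-in are missing from the planned safety tables

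*Combined protocol and SAP*

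**What the plan says.** The List of Abbreviations and Definitions of Terms gives the Full Analysis Set as "All enrolled patients who receive at least one dose of ABI-009 (treated population"). A nivolumab dose alone does not qualify.

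The synopsis (Statistical Considerations, Safety Analyses) says: "For the Phase 1 part of the study, the entire treated population (Full Analysis Set) will be the analysis population for all safety analyses". Section 8.2 has the same sentence for the other phase: "For the Phase 2 part of the study, the entire treated population (Full Analysis Set) will be the analysis population for all safety analyses". For Phase 1, Section 8.2 says only that "the following information will be reported for adverse events observed in the study: dose level" and further details will be given, and that paragraph names no population. No other safety set is defined.

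Nivolumab is given "q 3 weeks (Day 1 of every 21-day cycle"). On the second drug, the synopsis (Study Design) says "ABI-009 will start after 2nd nivolumab dose and will be administered on D8 and D15 beginning in C2"; Sections 2.3 and 6.1 agree.

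**The concern.** The set is described as everyone treated, yet its definition omits people who have had one or two infusions of a study drug. The definitions themselves treat nivolumab as study treatment, since they date end of treatment from the later of the two drugs. Someone taken off study treatment by severe toxicity in the lead-in, or who dies in it, enters neither numerator nor denominator of the tables built on this set.

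Exclusion of patients who progress before ABI-009 is at least disclosed, in the efficacy text. Exclusion for toxicity or death follows only from the definition.

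At stake is the description of the sequential regimen. The expansion part is meant to assess its overall safety, and Section 8.1 lists the frequency and grade of treatment-emergent adverse events as a secondary endpoint. A later user of this schedule would meet the lead-in risk without that selection.

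**Working it through.** The plan states no figure for the size of this loss, so there is none to reproduce. The check covers the timing, the likely number of patients, and the effect on a rate.

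**Timing.** Cycles last 21 days and ABI-009 starts on Cycle 2 Day 8. Counting Cycle 1 Day 1 as day 1, the first ABI-009 dose is on day (2 − 1) × 21 + 8 = 29, which is 28 days after the first nivolumab dose. Nivolumab has by then been given on days 1 and 22.

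**Expected number lost to toxicity.** The documents give no lead-in dropout rate. Section 1.3.3 reports, for the cited melanoma trial, "Nivolumab was discontinued for adverse reactions in 9% of patients", with a median exposure of 5.3 months. Assume a constant hazard:

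- 28 days = 28 / 30.4375 = 0.92 months
- q = 1 − 0.91^(0.92 / 5.3) = 0.016, or about 1.6%
- expected patients lost = N × q
- chance of at least one = 1 − (1 − q)^N

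With N = 40 to 50 (synopsis, Sample Size), and larger assumed values of q to allow for early deaths and other early stops:

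| Assumed q | Expected lost, N = 40 to 50 | Chance of at least one |
|---|---|---|
| 1.6% | 0.6 to 0.8 | 48% to 56% |
| 5% | 2.0 to 2.5 | 87% to 92% |
| 10% | 4 to 5 | over 98% |

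Only the first row is tied to a figure in the protocol. The others are assumptions.

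**Which events fall in the window.** In the cited trial the earliest of six immune-mediated pneumonitis cases came at 25 days, inside the lead-in, although the median was 2.2 months and the grade of that earliest case is not given. Section 6.3.2 lists Grade 3 or 4 pneumonitis among the reasons for permanently stopping nivolumab. Colitis began at 1 month and hepatitis at 86 days, so neither supports an exit before day 29.

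**Effect on a rate.** Take the 42% Grade 3–4 rate from Section 1.3.3 as an illustration among those in the set, and suppose that k excluded patients all had such an event. The rate among everyone treated is (0.42 × (N − k) + k) / N:

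- k = 1: 17.38 / 40 = 43.4%, or 21.58 / 50 = 43.2%
- k = 4: 19.12 / 40 = 47.8%, or 23.32 / 50 = 46.6%

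If one patient had a fatal adverse event in the lead-in, the fatal-event table would show none from the lead-in, where the rate among all treated is 1/50 to 1/40, or 2.0% to 2.5%.

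**The opposite direction.** Adding patients never given ABI-009 dilutes events that ABI-009 causes. With the 38% mucosal inflammation rate of the earlier ABI-009 phase 1 study (Section 1.2.4) and 4 unexposed patients among 40, the rate becomes 0.38 × 36 / 40 = 34%. A single wider denominator is therefore not a complete remedy.

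**The case against.** The strongest reply is that an ABI-009-treated set suits this trial. ABI-009 is the named investigational product, nivolumab is the approved agent, and the primary endpoint is the ABI-009 maximum tolerated dose. Lead-in events are recorded from consent, and serious events are reported within 24 hours whatever their cause. All analyses are descriptive, and the plan disclaims firm conclusions on safety. This stands as far as it goes: the primary endpoint is unaffected, and the loss is from the planned tables, not from collection or oversight. It does not answer the gap in describing the whole regimen.

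A reader might also infer more than the documents support:

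- **That every safety table in both phases is explicitly restricted.** The synopsis assigns the set to Phase 1 and Section 8.2 assigns it to Phase 2; both are covered only by reading the two together. The exposure summary names no population, so its loss of patients is an inference.
- **That only patients who tolerated the lead-in are reported.** Someone with lead-in toxicity who then receives ABI-009 stays in the set, with that event counted.
- **That 9%, or 4 to 5 patients, would be lost to toxicity.** The 9% built up over a median of 5.3 months. The median onsets of pneumonitis (2.2 months) and colitis (2.5 months) suggest that even a constant hazard may overstate the first 28 days for those events.
- **That early thyroid events are examples.** Section 6.3.1 calls for no nivolumab dose adjustment for them, so they would not ordinarily remove a patient.
- **That all rates are biased downwards.** This holds for the events that cause early exit, not for ABI-009-type events.

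**Conclusion.** The point holds and should be fixed, though it does not threaten the primary endpoint. As written, patients who stop or die before the first ABI-009 dose fall outside the only defined safety population, which the plan nonetheless describes as the whole treated population. The bias is downward for the events that cause early exit, including treatment-related deaths. Its size is uncertain and probably small: 0.6 to 0.8 patients of 40 to 50, with about an even chance of at least one. That rests on a constant hazard and on carrying a melanoma monotherapy figure, from an every-2-weeks schedule, over to this population. Early deaths and other early stops could raise it. Pneumonitis is the one immune event for which the protocol's own figures place a case inside the lead-in.

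**What to change.** 1. Define a safety set of all enrolled patients who receive at least one dose of nivolumab or ABI-009. Use it in both phases for the whole-regimen tables of adverse events, serious events, deaths and withdrawals, and for nivolumab exposure.
2. Split those tables by onset before or after the first ABI-009 dose.
3. Keep the ABI-009-treated set for dose-limiting toxicity, the maximum tolerated dose, and adverse event rates after ABI-009 starts, in Phase 2 as well as Phase 1, so that those rates are not diluted.
4. Reconcile the synopsis with Section 8.2 on which phase the safety population sentence covers.
5. Reconcile the end of adverse event recording and the timing of the end-of-treatment visit. Section 9.2 and footnote d of Table 2 tie them to the last ABI-009 dose. The synopsis ties recording to the last dose of investigational product, and the Definitions tie the visit to the later of the two drugs. Both must be defined for a patient who received only nivolumab.

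The cost is revised definitions, one extra table split, and possibly slightly less favourable adverse event rates. Recording already starts at consent, so items 1 to 4 need no new assessments; item 5 makes clear how long nivolumab-only patients are followed for safety.

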1. INTRODUCTION

1.1. Soft Tissue Sarcoma

Soft tissue sarcoma (STS) is a relatively rare neoplasm of mesenchymal origin, which includes a diversity of histological subtypes and occurs with an incidence of about 1% of all adult cancers. Surgical resection is still the treatment of choice for localized disease, along with radiation therapy for unresectable sarcomas. However, recurrence rate is high (~50%) and treatment options for metastatic/relapsed STS are limited to anthracycline-based chemotherapy (i.e., doxorubicin), administered alone or in combination with alkylating agents (ifosfamide and/or dacarbazine) (3, 4). Judging from studies conducted over the last 20 years, prognosis for advanced STS has been uniformly poor, with an estimated median survival of only 8 to 13 months (5-7). Recently, two new drugs for soft tissue sarcoma have been approved by the United States Food and Drug Administration (USFDA). The first drug, pazopanib (Votrient®, Novartis Pharma), is a multiple tyrosine kinase inhibitor, which hinders growth factor-mediated signal transduction pathways involved in tumor angiogenesis (8-10). The second drug, trabectedin/ET-743 (Yondelis®, Janssen Biotech, Inc.), is a natural alkaloid, originally isolated from the Caribbean tunicate, *Ecteinascidia turbinata*, which interacts with DNA in a complex manner that interferes with gene transcription and DNA repair (11). Following the approval of trabectedin in Europe for treatment-resistant STS (12, 13) and the results of a pivotal Phase 3 trial (14), which enabled its approval in the United States for liposarcoma and leiomyosarcoma in 2015, there is renewed optimism for improving the quality of life, progression-free survival, and potentially, the overall survival of advanced STS patients that have failed standard therapies (14, 15).

1.1.1 mTOR Inhibitors in Soft Tissue Sarcoma

Aberrant mammalian target of rapamycin (mTOR) signaling is common in sarcomas and other malignancies. Drug resistance and toxicities often limit benefits of systemic chemotherapy used to treat metastatic sarcomas. Ridaforolimus is an inhibitor of mammalian target of rapamycin, an integral component of the phosphatidyl 3-kinase/AKT signaling pathway, with early evidence of activity in sarcomas.

A multicenter, open-label, single-arm, phase II trial was conducted to assess the antitumor activity of ridaforolimus in patients with distinct subtypes of advanced sarcomas (Chawla et al. A total of 212 patients were treated in four separate histologic cohorts. In this heavily pretreated population, 61 patients (28.8%) achieved CBR. Median PFS was 15.3 weeks; median OS was 40 weeks. Response Evaluation Criteria in Solid Tumors (RECIST) confirmed response rate was 1.9%, with four patients achieving confirmed PR (two with osteosarcoma, one with spindle cell sarcoma, and one with undifferentiated pleomorphic sarcoma [formerly malignant fibrous histiocytoma]). Archival tumor protein markers analyzed were not correlated with CBR. Related adverse events were generally mild or moderate and consisted primarily of stomatitis, mucosal inflammation, mouth ulceration, rash, and fatigue. Conclusion: Single-agent ridaforolimus in patients with advanced and pretreated sarcomas led to PFS results that compare favorably with historical metrics.

A large randomized placebo-controlled phase III trial evaluated the mTOR inhibitor ridaforolimus to assess maintenance of disease control in advanced sarcomas after benefit from prior chemotherapy (16). Patients with metastatic soft tissue or bone sarcomas who achieved objective response or stable disease with prior chemotherapy were randomly assigned to receive ridaforolimus 40 mg or placebo once per day for 5 days every week. Primary end point was progression-free survival (PFS); secondary end points included overall survival (OS), best target lesion response, safety, and tolerability. A total of 711 patients were enrolled, and 702 received blinded study drug. Ridaforolimus treatment led to a modest, although significant, improvement in PFS per independent review compared with placebo (hazard ratio [HR], 0.72; 95% CI, 0.61 to 0.85; $P < .001$; median PFS, 17.7 v 14.6 weeks). Ridaforolimus induced a mean 1.3% decrease in target lesion size versus a 10.3% increase with placebo ($P < .001$). Median OS with ridaforolimus was 90.6 weeks versus 85.3 weeks with placebo (HR, 0.93; 95% CI, 0.78 to 1.12; $P = .46$). Adverse events (AEs) more common with ridaforolimus included stomatitis, infections, fatigue, thrombocytopenia, noninfectious pneumonitis, hyperglycemia, and rash. Grade 3 AEs were more common with ridaforolimus than placebo (64.1% v 25.6%). Conclusion: Ridaforolimus delayed tumor progression to a small statistically significant degree in patients with metastatic sarcoma who experienced benefit with prior chemotherapy. Toxicities were observed with ridaforolimus, as expected with mTOR inhibition. These data provide a foundation on which to further improve control of sarcomas.

Other mTOR inhibitors, including sirolimus and everolimus, have been tested or are being tested in clinical trials for advanced soft tissue sarcoma. For example, sirolimus, is currently approved for immunosuppression following organ transplantation. However, there is increasing interest in its role as a neoplastic agent. In a report of four cases of progressive metastatic sarcoma in patients who have progressed after 2–6 lines of chemotherapy, treatment with sirolimus resulted in minor radiographic improvement in three cases (17). Myxoid chondrosarcoma has also been reported to respond well to sirolimus in combination with cyclophosphamide (18).

Further, a phase II study investigating the efficacy of everolimus in patients with histological evidence of progressive or metastatic bone or soft tissue sarcoma is currently underway (19), as is a phase I/II study of everolimus in pediatric patients with recurrent or refractory solid tumors (20).

